8.5 Visits

Visit 2, Week 6 ± 1 week

Participants may find the assessment sessions to be tiring and small breaks should be provided when needed. Children will be asked to complete:

1. Stanford Sleepiness Scale
2. Tea-Ch2 selective and sustained attention subtests
3. Child ANT and Anticipated Response Task

Break if needed

4. Corsi Block-Tapping Test
5. Digit Span task

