6.2 Intervention(s)

Intervention/TALI group

The intervention/TALI group will complete the TALI Attentional Training Program (TALI Train). TALI Train is a gamed-based computerised task, delivered on a tablet. The TALI program comprises four different activities, each lasting 4 minutes in duration. Each activity requires children to utilise a different attentional skill; selective attention, sustained attention, attentional control, and response inhibition respectively. Children may complete the four activities in any order, but must complete all activities each session. As children progress through the levels within the activity, the tasks become more difficult. TALI has been designed to be adaptive and therefore when children respond incorrectly, or fail to respond, prompts are given and levels become easier until the child again begins

to record correct responses. Children are rewarded for successful completion of an activity with a virtual toy. Each day the child recommences the activities at the level they finished on during their last session. Sessions take 20 minutes to complete. The TALI program is designed so that children are locked out until midnight following completion of a session, to ensure that only one session is completed per day. Children will be required to complete five 20 minute sessions per week for five weeks.

Following the initial assessment, children and parents will be set up on the TALI system and provided with a tablet to use for the duration of the intervention. Following this, children will be asked to continue to use TALI for the above specified timeframe. Parents are asked to supervise each training session. Sessions can be completed in the home and do not require an internet connection. Each week families will receive a phone call from the unblinded member of the research team to address any questions or concerns raised. If the family do connect to the internet during the intervention delivery, data will automatically be uploaded to the secure TALI platform to be accessed by the unblinded member of the research team. This will allow researchers to monitor compliance, and also address concerns raised by parents. The TALI train program will be used in the default mode to ensure consistent setting for all children in the trial.

Active Control Task/Control Group

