8 STUDY VISITS AND PROCEDURES

8.1 Study timeline

8.2 Schedule of assessments

Time point relative to randomisation		
Screening		A
Screening		B
Randomisation (0 week)	Intervention	Control
Pre-intervention assessment (1 week)	C	C
Training in intervention (1 week)	D	E
Completion of intervention (1 week to 5 weeks)	F H	G H
Post-intervention assessment (5 weeks)	C	C
Post-intervention assessment (3 months)	C	C
Post-intervention assessment (6 months)	C	C
TALI offered to control group (6 months)		I
Intervention (6 months to 7 months)		F
A	Questionnaire screening for attentional deficits, and other inclusion/exclusion is emailed to families for completion.	
B	Screening for IQ criteria completed for children who have not undergone IQ testing post injury, or within the past two years.	
C	A face to face assessment session (2 - 2.5 hours) is held at MCRI. A researcher will administer the SSS, TEA-Ch2 selective attention and sustained attention subtests, the child ANT, the Anticipated Response Task, the Corsi Block-Tapping Test, a digit span task, the PEERS, the WIAT-II, and the IMS (pre-intervention only). Parents will be asked to complete the SWAN, the CSHQ, the PECL, the GHQ-12, the CDS-P, the SCAS-P, and the PEERS-Q.	
D	Parents and children will be trained in the use of the TALI program. Researchers will provide a tablet with the intervention program and parent guidebook.	
E	Parents and children will be trained in the use of the control task program. Researchers will provide a tablet with the control program and parent guidebook.	
F	Children will complete TALI modules for 20 mins per day, 5 days per week for 5 weeks, under the supervision of a parent.	
G	Children will complete control task modules for 20 mins per day, 5 days per week for 5 weeks, under the supervision of a parent.	
H	Families will receive weekly phone contact from a researcher to offer support throughout the intervention, address any technical issues that arise, and to monitor compliance.	
I	Families in the control group will be offered access to the TALI program.	

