8.4 Baseline

Enrollment/Baseline Visit (Visit 1, Week 1)

Pre-intervention assessments will be conducted by [name], [name], [name] or an MCRI research assistant. These assessments will take place at MCRI. Participants may find the assessment sessions to be tiring and small breaks should be provided when needed. The assessments will comprise the following tasks and are estimated to take 2 – 2.5 hours to complete:

1. Stanford Sleepiness Scale – The SSS is a single item self-report assessment of current levels of sleepiness. Children are asked to rate their current level of sleepiness on a 7 point scale ranging from 1 (very awake) to 7 (very sleepy). This measure is expected to take no more than 5 minutes to complete.
2. Test of Everyday Attention for Children (Tea-Ch2) will be used to assess attention. Children aged 4 to 7 will complete 4 subscales from junior version which are either facilitated by or wholly completed on the computer. The subtests are designed to assess selective attention (Balloon Hunt; Balloons 5) and sustained attention (Simple Reaction Time; Sustained Attention to Response Task). Children aged 8 to 9 years will complete 4 equivalent subscales from the older version (Hector Cancellation; Hector-B; Simple RT and SART). The battery should take no more than 20 minutes to complete. This measure provides both raw score and scaled scores for each of the subtests.
3. Child Attention Network Task (ANT) – a child friendly version of the flanker task which is suitable for children aged 4 years and above. The Anticipated Response task - a stop signal task that measures the ability to rapidly prevent already initiated actions. The Child ANT would enable assessment of interference control and the Anticipated Response task assessment of response inhibition, both aspects of attentional control. These measures are administered on a laptop and should take no more than 30 minutes in total to complete.
4. Corsi Block-Tapping Test (forwards and backwards) – Visuospatial working memory. Children are required to replicate a sequence by clicking the corresponding blocks on the screen. This test is administered on a laptop and should take no more than 10 minutes to complete. This measure provides a raw score of the number of sequences children have correctly replicated.

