8.11 Continuation of therapy

After the 5-week intervention period, participants will be unable to access their assigned program. Researchers will collect the tablet devices that contain the assigned program at the post intervention assessment.

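### The Visit 2 window opens a week before the five-week programme ends, and the schedule table and the adherence split need matching corrections

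*Protocol*

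**What the plan says.** - **Baseline and hand-over.** Section 8.4 is headed "Enrollment/Baseline Visit (Visit 1, Week 1"), and the family receives the tablet once that assessment is finished.
- **Dose.** Section 6.2 states for the TALI arm: "Children will be required to complete five 20 minute sessions per week for five weeks". The control arm has the same schedule. Notes F and G in section 8.2 repeat it; note F reads "Children will complete TALI modules for 20 mins per day, 5 days per week for 5 weeks, under the supervision of a parent".
- **Post-training visit.** Section 8.5 gives "Visit 2, Week 6 ± 1 week".
- **End of access.** Section 8.11 says "After the 5-week intervention period, participants will be unable to access their assigned program", and has the tablets collected at the post-intervention assessment. Section 15 puts their return about five weeks after the pre-intervention assessment.
- **Schedule table.** The table in 8.2 is headed "Time point relative to randomisation". It puts baseline at 1 week and lists "Completion of intervention (1 week to 5 weeks") and then "Post-intervention assessment (5 weeks").
- **Compliance.** Section 6.2.2 counts a child as compliant at 20 of 25 sessions. Section 13.2.2 compares children with fewer than 20 sessions against those with more than 20.

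**The concern.** The primary outcome in section 9.1 is the between-group comparison at post-training. Under the stated window a child can be tested, and give the tablet back, with the fifth week of training still to do. That visit would be within protocol, so no deviation would be recorded, and the missing sessions could not be made up afterwards.

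Two other entries touch the same point. The table in 8.2 puts the post-intervention assessment at 5 weeks, where 8.5 says Week 6. The adherence split in 13.2.2 leaves a child with exactly 20 sessions in neither group, and 20 is the count an on-pace child reaches at the early edge of the window.

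**Working it through.** **Inputs.** Hand-over at Week 1 (8.4); 5 sessions a week for 5 weeks (6.2); Visit 2 at Week 6, plus or minus 1 week (8.5); compliance at 20 sessions (6.2.2); at most one TALI session a day (6.2).

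**The plan's own figure.** 5 sessions × 5 weeks = 25, the maximum given in 6.2.2.

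**End of training.** Week 1 + 5 weeks = Week 6.

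**Sessions available by visit date.** Weeks available = visit week − 1; scheduled sessions = the smaller of 25 and 5 × weeks available.

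| Visit 2 at | Weeks since hand-over | Days | Scheduled sessions |
|---|---|---|---|
| Week 5 | 4 | 28 | 20 |
| Week 6 | 5 | 35 | 25 |
| Week 7 | 6 | 42 | 25 |

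**Loss at the early edge.** 25 − 20 = 5 sessions; 5/25 = 20%.

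**Margin against the compliance rule, without catch-up sessions.** Over five weeks a child can miss 25 − 20 = 5 sessions and still comply. At the early edge the margin is 20 − 20 = 0.

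**Catch-up.** At one session a day, 28 days are enough for 25 sessions (25/4 = 6.25 a week, above the prescribed 5). The loss can therefore be zero.

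**Calendar-week reading.** Suppose Week 1 means days 1 to 7 and Week 5 means days 29 to 35. The gap from hand-over to visit is then between 29 − 7 = 22 and 35 − 1 = 34 days, always under 35. Even Week 6 (days 36 to 42) can fall 36 − 7 = 29 days after hand-over. So this reading does not remove the problem, and it is a reason to count the window from the hand-over date.

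**Table in 8.2.** Read as elapsed time from randomisation, 5 − 1 = 4 weeks separate baseline from the post-intervention assessment. That is 4 × 5 = 20 sessions, and it conflicts with the five weeks in 8.5 (6 − 1) and in section 15.

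**Adherence split.** 6.2.2 treats 20 as compliant. In 13.2.2, 20 is neither below 20 nor above 20.

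**The case against.** The intention is clear. Section 8.11 ends access after five weeks, section 15 has the tablet back at about five weeks, and the table in 8.2 lists completion of the programme before the assessment. The plus or minus one week can be read as ordinary scheduling tolerance, since Visits 3 and 4 carry the same. An unblinded researcher telephones every family weekly and would know whether a child had finished. An on-pace child seen early still meets the 20-session rule. The 5-week row may mean the end of calendar week 5, or may simply name the visit, as 13.2.3 does when it speaks of a 5-week follow-up. The more-than-20 wording is an evident slip that 6.2.2 resolves.

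Much of this stands, and it keeps the point small. The table row taken alone is a labelling fault, and the adherence slip is separate from the window. But none of these passages bars a Week 5 visit, and nothing links the weekly calls to the booking of Visit 2. Whoever schedules from 8.5 may book a child before the fifth week is done.

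**Conclusion.** The concern holds and is minor. Section 8.5 permits the post-training assessment up to one week before five weeks of training have passed. For a child on the prescribed pace that costs up to 5 of 25 sessions (20%); for a child who trained daily it may cost none. These figures take the week numbers as elapsed weeks from randomisation, the origin used in 8.2. On calendar weeks the exact shortfall varies, but a Week 5 visit is always early.

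With a shared window and blinded assessment, the likely result is a small dilution of the treatment contrast, not bias. Its size cannot be estimated, because the protocol does not say how many children would be seen early. The error at exactly 20 sessions affects only the preliminary adherence comparison, not the intention-to-treat analysis.

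**What to change.** - **8.5:** open the Visit 2 window no earlier than five weeks (35 days) after tablet hand-over. Week 6, 0 to +1 week, is the cleaner choice.
- **8.2:** show five weeks of training starting at the baseline visit, and the post-intervention assessment at week 6.
- **13.2.2:** define the adherent group as 20 or more sessions.

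The cost is a few words in one window, two table rows and one inequality, plus ethics approval if the change counts as an amendment under 14.2. No visits or data are added.

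The trade-off is flexibility. A window of 0 to +1 week is half the present two-week width, for sessions of 2 to 2.5 hours at one site. A window of 0 to +2 weeks keeps the width, and 8.9.2 already waits two weeks past the scheduled date before a visit counts as missed. But it allows testing up to two weeks after training ends, and Visit 2 at Week 8 could fall 12 − 8 = 4 weeks before the earliest Visit 3, against 12 − 7 = 5 weeks now.

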6. PEERS
7. WIAT II

Parents will be asked to complete:

1. SWAN
2. CSHQ
3. PECCI
4. GHQ-12
5. CDS-P
6. SCAS-P
7. PEERS-Q

Visit 3, Week 13 ± 1 week

Participants may find the assessment sessions to be tiring and small breaks should be provided when needed. Children will be asked to complete:

1. Stanford Sleepiness Scale
2. Tea-Ch2 selective attention and sustained subtests
3. Child ANT and Anticipated Response Task

Break if needed

4. Corsi Block-Tapping Test
5. Digit Span task
6. PEERS
7. WIAT II

Parents will be asked to complete:

1. SWAN
2. CSHQ
3. PECCI
4. GHQ-12
5. CDS-P
6. SCAS-P
7. PEERS-Q

8.6 Final study visit

Visit 4, Week 26 ± 1 week

Participants may find the assessment sessions to be tiring and small breaks should be provided when needed. Children will be asked to complete:

1. Stanford Sleepiness Scale
2. Tea-Ch2 selective and sustained attention subtests
3. Child ANT and Anticipated Response Task

Break if needed

4. Corsi Block-Tapping Test
5. Digit Span task
6. PEERS
7. WIAT II

Parents will be asked to complete:

1. SWAN
2. CSHQ
3. PECI
4. GHQ-12
5. CDS-P
6. SCAS-P
7. PEERS-Q

After completing the above measures, parents and children will then be asked to complete a questionnaire, asking them to indicate whether they thought they had been allocated to the TALI program group or the control group.

Following this visit, parents of children in the control group will be contacted and offered access to the TALI train program by an unblinded member of the research team.

Parents will be advised that they will receive a 6 monthly newsletter outlining the study progress, and at the completion of the study they will receive an invitation to an information session where researchers will present the findings of the study.

8.7 Withdrawal

Given that the assessments are the same for each of the time points it is unlikely that a participant will wish to complete the assessment if they chose to withdraw or if the project ends early. All participants will be provided with results from the assessments after each timepoint, if they wish.

8.8 Unscheduled visit

Although unscheduled visits are unlikely, all contact with participants and their families will be documented by researchers on the CRF.

8.9 Participant Withdrawal

8.9.1 Reasons for withdrawal

The investigators may withdraw a participant from the study intervention if the participant:

- Experiences a subsequent brain injury
- Commences chemotherapy
- Undergoes any neurosurgical intervention or treatment
- Commences medication for the purpose of treating inattention
- Commences any therapy or other intervention for the purpose of treating inattention
- Is in violation of the study protocols
- Experiences a serious or intolerable adverse event
- Experiences a decline in wellbeing.

The investigators will also withdraw all participants from the study intervention if the study is terminated. Participants are free to withdraw from the study at any time upon their request. Withdrawing from the study will not impact their ability to access interventions in future, nor will this affect their relationship with the hospital.

8.9.2 Handling of withdrawals and losses to follow-up

When a participant withdraws from the study, the reasons for withdrawal shall be recorded by the investigator on the relevant page of the CRF. Participants who fail to return for study assessments will be contacted by the research team in an attempt to have them comply with the protocol. This will entail two documented phone calls and one registered letter. If a period greater than 2 weeks has passed from the scheduled assessment date then participants will be recorded as having “missed” this assessment.

8.9.3 Replacements

The study will continue to recruit participants for a period for 12 months with the aim of achieving the required sample size.

8.10 Trial Closure

If the study is terminated prematurely, then all participants will be contacted via phone to explain the reasons for termination and the impact this may have on them. Termination or extension of the study can only be made by the Chief Investigator, in this case [name].

8.11 Continuation of therapy

After the 5-week intervention period, participants will be unable to access their assigned program. Researchers will collect the tablet devices that contain the assigned program at the post intervention assessment.

9 OUTCOMES

9.1 Primary outcome

The primary outcome is an improvement in cognitive attention, as measured by the Test of Everyday Attention for Children (selective and sustained attention) and experimental paradigms of attentional control (interference control with the Child ANT test and response inhibition with the anticipated response task) between the intervention and control group at post-training.

9.2 Secondary outcome(s)

The secondary outcome measures are as follows;

- Behavioural attention as measured by the SWAN

- Visuospatial working memory as measured by the Corsi Block-Tapping task
- Auditory working memory as measured by the digit span task
- Social skills as measured by the PEERS
- Mathematics ability as measured by the WIAT-II

10 ADVERSE EVENTS AND RISKS

10.1 Definitions

Unanticipated Problems

Unanticipated problems involving risks to participants or others to include, in general, any incident, experience, or outcome that meets all of the following criteria:

- unexpected in terms of nature, severity, or frequency given (a) the research procedures that are described in the protocol-related documents, and (b) the characteristics of the participant population being studied;
- related or possibly related to participation in the research; and
- suggests that the research places participants or others at a greater risk of harm (including physical, psychological, economic, or social harm) than was previously known or recognised

Adverse Event (AE)

Any untoward medical occurrence in a patient enrolled into this study regardless of its causal relationship to study/interventions.

Serious Adverse Event (SAE)

Adverse events are classified as serious or non-serious.

An SAE is defined as any AE that:

- results in death; or
- is immediately life threatening; or
- requires inpatient hospitalisation; or
- requires prolongation of existing hospitalisation; or
- results in persistent or significant disability/incapacity; or
- is a congenital anomaly/birth defect.

Important medical events will be considered an SAE when, based upon appropriate medical judgement, they may jeopardise the patient and may require medical or surgical intervention to prevent one of the outcomes listed in this definition.

10.2 Assessment and documentation of adverse events

If researchers notice a decline in the child's or parent/caregivers wellbeing during weekly check-ins, or during follow up assessment they are able to provide a referral to an appropriate service for support. Alternatively where the child is currently receiving care from another department, permission may be sought to notify the child's treating clinician to ensure that support is being provided. Researchers will notify the PI's [name] and [name] of any declines in wellbeing identified, and a determination will then be made whether it is in the child's best interests to be withdrawn from the study. Any concerns and outcomes will be recorded in the participant's CRF. Serious adverse events

will be reported to the HREC within 24-72 hours of occurrence. Families are reminded that they may withdraw from the study at any time.

For the purposes of this study the investigator is responsible for recording all Adverse Events, regardless of their relationship to study intervention, with the following exceptions:

- Conditions that are present at screening and do not deteriorate will not be considered adverse events.

The description of each AE on the CRF will include:

- A description of the AE;
- The onset date, duration, date of resolution;
- Severity (mild, moderate or severe);
- Any action taken;
- The outcome (recovery, death, continuing, worsening);
- The likelihood of the relationship of the AE to the study intervention (Unrelated, Possible, Probable, Definite).

The severity and relationship of an AE will be assessed as per appendix D. The seriousness of an AE will be assessed by an investigator according to the definition in section 9.1

Changes in the severity of an AE will be reported. AEs characterised as intermittent will be documented for each episode. All AEs will be followed to adequate resolution, where possible.

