6.2.1 Modification

Not applicable. Once children have been allocated to either TALI Train or the active control program there will be no change in group allocation. If children or parents do not wish to continue with their allocated program they will be able to withdraw from the study.

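### For a decline in wellbeing, 8.9.1 provides for stopping the intervention but 10.2 decides on leaving the study, and nothing says the child stays in follow-up

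*Protocol*

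**What the plan says.** Section 8.9.1 opens its list with "The investigators may withdraw a participant from the study intervention if the participant", and the last item is "Experiences a decline in wellbeing". The same section then treats leaving the study as a different matter, decided by the family: "Participants are free to withdraw from the study at any time upon their request".

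Section 10.2 covers declines noticed at weekly calls or follow-up assessments. Staff may refer the family or, with permission, notify the treating clinician. They report any decline to the principal investigators, after which "a determination will then be made whether it is in the child's best interests to be withdrawn from the study".

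Three other sections bear on what happens next:

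- 6.2.1, on families who want to stop the program: "If children or parents do not wish to continue with their allocated program they will be able to withdraw from the study".
- 8.7, on assessments at withdrawal: "it is unlikely that a participant will wish to complete the assessment if they chose to withdraw".
- 8.9.2 has the reason for withdrawal recorded, and provides two phone calls and a registered letter for participants who fail to return for assessments.

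On analysis, 13.2.1 promises an intention-to-treat approach covering all enrolled children. Section 13.2.2 offers regression imputation (under 20% missing and missing completely at random) or Expectation Maximisation (missing at random).

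**The concern.** Stopping a treatment and stopping data collection are different decisions, and 8.9.1 itself keeps them apart. Section 10.2 merges them for one trigger. An investigator who follows 10.2 as written is asked whether the child should leave the study, when the safety question is usually whether the child should stop the program.

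At stake are the outcomes of children who do badly. If they leave the study, their later scores are never measured, and no analysis method can recover them. An intention-to-treat analysis then rests on imputed values for the children whose course is least predictable from what was observed.

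The timing adds to this. Section 8.11 says that "After the 5-week intervention period, participants will be unable to access their assigned program". Once the program is over, leaving the study cannot reduce exposure to it. It ends outcome collection and spares the child later assessments.

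**Working it through.** **1. The two provisions side by side.**

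- Event: a decline in wellbeing, in both 8.9.1 and 10.2.
- Object of the decision: the study intervention in 8.9.1; the study in 10.2.
- Force: discretionary in both. 8.9.1 says the investigators may act; 10.2 calls for a case-by-case judgement.
- Follow-up afterwards: stated in neither. The visit schedule in 8.5 and 8.6 is not made conditional on continuing the program, so a child withdrawn only from the intervention could be read as still scheduled. No sentence says so.

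**2. Visits lost, by time of removal.** The post-baseline visits are weeks 6, 13 and 26 (8.5, 8.6).

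- Removed in weeks 1 to 5: 3 of 3 lost, including the post-training visit that defines the primary outcome (9.1).
- Removed at the week 6 visit: 2 of 3 lost.
- Removed at the week 13 visit: 1 of 3 lost.

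**3. Fit with the imputation in 13.2.2.** Removal triggered by the child's condition is not missing completely at random on its face. Missing at random would require the observed data to account for the loss. A child removed in weeks 1 to 5 has only baseline outcome scores, so neither regression imputation nor Expectation Maximisation has any outcome measured after the decline to work from.

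**4. A scale for the possible effect.** The point carries no figure of its own. The planning effect in 13.1 gives a yardstick, and its sample sizes reproduce. With λ = N·f²·m / (1 + (m − 1)·ρ), m = 2, ρ = .5, alpha .05, and 1 and N − 2 degrees of freedom:

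- f = .4, N = 40: λ = 40 × 0.16 × 2 / 1.5 = 8.53, power 0.812.
- f = .25, N = 98: λ = 98 × 0.0625 × 2 / 1.5 = 8.17, power 0.808.

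These are the smallest even N reaching 80% power, as 13.1 states. For two groups d = 2f, so the medium effect is d = 2 × 0.25 = 0.5.

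**5. Illustration under assumptions.** The protocol gives no withdrawal rate. Suppose one arm of 40 loses k more children than the other before week 6, and their unseen scores would have been δ SD worse than those of the children who stay. If those who stay stand in for all, that arm's mean is overstated by k·δ/40:

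- k = 0 (balanced losses, same δ): 0.
- k = 2, δ = 0.5: 2 × 0.5 / 40 = 0.025 SD, which is 0.025 / 0.5 = 5% of d.
- k = 4, δ = 1: 4 × 1 / 40 = 0.10 SD, 20% of d.
- k = 6, δ = 1: 6 × 1 / 40 = 0.15 SD, 30% of d.

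A simulation (20,000 runs, n = 40, baseline correlation .5, regression imputation from baseline) gave 0.025, 0.100 and 0.151. It assumes the decline is unrelated to baseline, so imputation from baseline could not have helped. It confirms the arithmetic and is not independent evidence of bias. Expectation Maximisation was not simulated.

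**6. Precision.** Under the 13.1 model with f = .25, power is 0.722 with 80 children, 0.700 with 76 and 0.676 with 72, if lost children contributed nothing. These losses are also assumed, and a growth model that used partial data would lose less.

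**The case against.** The strongest reply is that the passages are compatible. Investigators may stop the program under 8.9.1, and the principal investigators may separately consider under 10.2 whether taking part still serves the child. Section 10.2 mentions referral and the treating clinician first and sets no default of removal. Leaving the study can be right for a particular child, since assessments run 2 to 2.5 hours and may be tiring. All of this stands. What remains is that 10.2 names only the more drastic decision, and the consequence of the milder one for follow-up is unwritten.

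A reader might infer more than the documents support:

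- *That intention to treat is contradicted.* Section 13.2.1 concerns who is analysed. A withdrawn child can still enter through baseline data and imputation, so the promise is weakened only indirectly.
- *That 6.2.1 and 8.7 end follow-up for such a child.* Both concern families who choose to leave. The first is a permission and the second a prediction; neither bars assessment nor addresses an investigator's decision.
- *That a caregiver's decline also triggers withdrawal.* The caregiver appears in the referral sentence ("parent/caregivers wellbeing during weekly check-ins, or during follow up assessment they are able to provide a referral"), while the withdrawal test is the child's best interests.
- *That losses will differ by arm because the weekly caller is unblinded.* The caller may notice the decline, but the determination follows notification of the principal investigators. Nothing says the arm is disclosed, and 7.2.1 restricts unblinding. Differential loss is possible but not shown.
- *That many visits are affected.* Weeks 6 and 13 give at most 80 × 2 = 160 visits at which the program is already over. That counts occasions and is not an expected loss.

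It is also fair that 6.2.3, which excludes from the trial children who start attention therapy or medication, conflicts more firmly with 8.9.1, where the same events lead to intervention withdrawal. That is a separate instance of the same undefined distinction and does not cure this one.

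**Conclusion.** The point holds as a mismatch with a missing default. For one event, 8.9.1 speaks of stopping the intervention and 10.2 of leaving the study, and no section states that a child taken off the program continues the scheduled assessments. Following 10.2 can therefore end outcome collection by investigator decision, costing between one and three of the three post-baseline visits, for a reason that sits badly with the assumptions in 13.2.2.

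The size of any bias is unknown. The range of 0.025 to 0.15 SD rests wholly on assumed values of k and δ; k = 6 would mean an excess of 15% of one arm (6/40) removed before week 6, and nothing in the protocol suggests that rate. With few or balanced withdrawals the effect is negligible. The case for changing the text is that the loss is avoidable and the change is cheap. The documents do not show that the trial's result is in danger.

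**What to change.** In 10.2, make the determination whether the child should be *withdrawn from the study intervention (8.9.1)*.

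In 8.9.2, add: *Stopping the study intervention does not end participation. The child is invited to all remaining scheduled assessments, shortened or omitted where too burdensome, unless the guardian withdraws consent or the principal investigators judge continued participation itself to be harmful. The latter is recorded as a separate reason.*

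Align 6.2.1 and 8.7 with that rule, so that a family wishing to stop the program is offered continued assessment before leaving the study. Check the new sentence against 6.2.3, which would otherwise still exclude some of these children from the trial.

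The cost is an amendment with ethics committee approval under 14.2. No visits or measures are added. The downside is that a 2 to 2.5 hour assessment may weigh on a family in difficulty, which is why the text allows shortening, omission and full withdrawal. Referral and notification of the treating clinician stay as they are.
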